## **6.8 Maximum Dose and Use of Adjunctive Phenobarbital**

Rescue doses of buprenorphine cannot be given when at maximum dose of 25 mcg/kg. Maximum dose will be defined by the actual weight at the time of dose administration. When the maximum dose of buprenorphine (75 mcg/kg/day) has been achieved, phenobarbital will be initiated with a loading dose of 20 mg/kg followed by 5 mg/kg/day. If symptoms of NAS are not controlled with phenobarbital 5 mg/kg/day, this can be titrated up by the treating physician to a serum concentration of 20-40 mg/dL. If symptoms are not controlled at 5 mg/kg/day, the attending physician may adjust the dose clinically as needed, with or without the use of phenobarbital therapeutic drug monitoring.

Treatment with adjunctive phenobarbital will continue for at least two days. When buprenorphine has been weaned to at least 50% of the maximal dose and the sum of the previous three scores is  $< 18$  and no single score is  $\geq 8$ , the attending physician will decrease the phenobarbital dose to 2.5 mg/kg/day. The buprenorphine dose will not be changed when phenobarbital is weaned. The half-life of phenobarbital in neonates decreases from 115 hr after 1 week to 67 hr after 4 weeks. As such, phenobarbital will be continued for three dose or interval titrations. When the sum of the previous three scores is  $< 18$  and no single score is  $\geq 8$ , the attending physician may discontinue phenobarbital. The buprenorphine will not be

weaned on the step when phenobarbital is discontinued.

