#### 1.3.4.3 Simulated Uptitration

The BBORN trial used an uptitration rate of 25%. A 33% and 50% up-titration rate were simulated (Table 4, reference in shaded box) at the 8 mcg/kg q8 initial dose. The endpoint was time to stabilization, defined as 48 hours without need for up-titration of dose.

Table 4: Simulated Time to Stabilization (hours) with Varied Uptitration Rate

Initial dose (mcg/kg)	Time to stabilization (hours)			$\Delta$ time to stabilization from reference 25% uptitration rate (hours)	
	Titration rate			Titration rate	
	25%	33%	50%	33%	50%
5.3	153.8	139.2	126.0	-14.6	-27.8
8.0	137.3	131.5	118.0	-5.8	-19.3

*Shaded box represents the dose regimen used in the BBORN trial.*

Both 33% and 50% provide advantages over the 25% uptitration rate in meeting the time to stabilization. However, as a higher initial dose is being used, the use of a 50% uptitration rate would entail large, rapid increase in exposures. In the BBORN trial there were 6 titrations before maximum dose was reached. Even with increasing the maximum dose, the number of titrations before need for a secondary agent drops. At a 50% increase, maximum dose is reached after only three uptitrations. (Table 5)

Table 5. Uptitration Steps to Maximum Dose

Uptitration rate	Initial dose (mcg/kg)	Uptitration step						Max daily dose (mcg/kg)
		1	2	3	4	5	6	
25%	5.3	6.6	8.3	10.4	12.9	16.2	20.0	60.0
25%	8	10.0	12.5	15.6	19.5	25.0		75.0
33%	8	10.6	14.2	18.8	25.0			75.0
50%	8	12.0	18.0	25.0				75.0

*Shaded row represents the dose regimen used in the BBORN trial.*

Based on the favorable simulated efficacy advantages, combined with a conservative approach to rate of increase and ability to titrate before reaching maximum dose and need for adjunctive phenobarbital, a uptitration rate of 33% will be used.

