## **3 OVERALL DESIGN AND PLAN OF THE STUDY**

### **3.1 Overview**

This is a single-site, open label clinical trial. Potential patients will be identified in the prenatal period by staff of the Thomas Jefferson University Family Center and by daily screening of the inpatient census at Thomas Jefferson University Hospital. Infants at risk for NAS will have abstinence assessed using the MOTHER scoring instrument, which is based upon Finnegan Score and will hereafter be called the “NAS score” (Appendix 1). This is the standard instrument used at Thomas Jefferson University Hospital. A need for initiation of treatment will be defined as any consecutive 3 scores adding up to  $\geq 24$  or any single score  $\geq 12$ , and the clinical decision of the attending physician that the infant requires pharmacologic therapy (Figure 2). When the threshold for initiation of treatment is reached, a re-review of inclusion and exclusion criteria will take place prior to dose administration. NAS scores will be obtained every 4 hours. Dose assessment will take place daily. If the three previous NAS scores are  $\geq 24$ , a dose advancement will take place (at the discretion of the neonatologist). Buprenorphine dose will be increased by 33% per uptitration. After two days of stability, patients will have weaning of dose until initial dose is reached.

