### **3.2.4.3 Need for Supplemental Phenobarbital Use**

Phenobarbital is used as a rescue therapy when maximum opioid replacement therapy dose is reached without adequate resolution of symptoms. The number of infants requiring phenobarbital rescue will be recorded.

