### **6.4 Dose Escalation**

Dose escalation of 33% of the previous dose will take place if

- the sum of 3 NAS scores is  $>24$  or a single score is  $>12$   
OR
- a rescue dose was administered [section 6.5].

To mimic actual clinical care, dose advancement will generally take place in daylight hours when the primary team caring for the patient is present. However, dose advancement may take place when the primary team is not present (such as would occur on evenings and nights). All dose decisions will be made based on the three most recent scores. No more than one dose escalation can take place each day, unless there is need for an additional rescue dose post-escalation.

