### **6.5 Rescue Dose**

If, between scheduled doses, a child has a single score of  $\geq 12$ , a rescue dose may be administered at the discretion of the treating physician. The rescue dose will be same as the previous dose. A rescue dose must be given at least 1 hour after and 1 hour before the next scheduled dose.

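### Sections 6.8 and 3.2.4.3 disagree on when phenobarbital starts, and sections 3.1 and 6.4 disagree on when the dose is raised before weaning

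*Protocol*

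**What the plan says.** **Phenobarbital.** Section 6.8: "When the maximum dose of buprenorphine (75 mcg/kg/day) has been achieved, phenobarbital will be initiated". Section 3.2.4.3: "Phenobarbital is used as a rescue therapy when maximum opioid replacement therapy dose is reached without adequate resolution of symptoms", followed by the exploratory endpoint: "The number of infants requiring phenobarbital rescue will be recorded". The rationale for the up-titration rate in 1.3.4.3 mentions the two events together ("ability to titrate before reaching maximum dose and need for adjunctive phenobarbital") without saying whether one implies the other.

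**Dose advancement before weaning.** Section 3.1 sets a threshold of at least 24 on the three previous NAS scores, at which "a dose advancement will take place (at the discretion of the neonatologist". Section 6.4 begins "Dose escalation of 33% of the previous dose will take place if" and lists a sum of three scores above 24, a single score above 12, or a rescue dose having been given. It says nothing about discretion. Under 6.5, after a single score of at least 12 between scheduled doses, "a rescue dose may be administered at the discretion of the treating physician".

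The version table for 1.1 records no change to any of these rules, so both differences stand in the current text.

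**The concern.** These rules decide who receives a second drug and who has the dose raised, and staff cannot follow both members of either pair in every case.

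The phenobarbital rule also defines an endpoint. Under 3.2.4.3 the count measures failure of the maximum buprenorphine dose to control symptoms. Under literal 6.8 it measures how many infants were titrated to the maximum, whatever happened there. These are different quantities reported under one label. The same rule decides which infants fall under the co-administration row of the sampling schedule (Table 9).

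The escalation rule matters at the boundary. NAS scores are whole numbers, so a sum of exactly 24 can occur, and the two sections then give different answers. Raising the dose also restarts the 48 hours without advancement that 6.6 requires before weaning.

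**Working it through.** **1. Can an infant be at the maximum and controlled?** Inputs: initial unit dose 8 mcg/kg, up-titration 33%, maximum unit dose 25 mcg/kg every 8 hours (Tables 1 and 5). Formula: dose after step k = 8 × 1.33^k.

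- k = 1: 10.64
- k = 2: 14.15
- k = 3: 18.82
- k = 4: 25.03

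This reproduces the Table 5 row (10.6, 14.2, 18.8, 25.0). The daily maximum is 3 × 25 = 75 mcg/kg. An infant takes the fourth step because of scores or a rescue dose at 18.8 mcg/kg. The response to 25 mcg/kg is not known at that moment, so control at the maximum is possible.

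**2. The two phenobarbital rules applied to an infant at the maximum.**

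| State at the maximum | 6.8 | 3.2.4.3 |
|---|---|---|
| Symptoms not adequately resolved | starts | starts |
| Symptoms controlled | starts | does not start |

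The sections differ only in the second row. The planned sample is 10 infants (Synopsis), so each infant in that row changes the count by 1/10 = 10 percentage points. The protocol gives no expected number of such infants. The only bound is the trivial one of 0 to 10, which is not a forecast.

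**3. The two escalation rules applied to example scores, before weaning.** Section 3.1 literally refers to the three scores being at least 24. I read this as their sum, in line with the initiation rule in the same section.

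| Scores | Sum | Highest | 3.1: sum ≥24 | 6.4: sum >24 | 6.4: single >12 |
|---|---|---|---|---|---|
| 8, 8, 8 | 24 | 8 | met | not met | not met |
| 12, 6, 6 | 24 | 12 | met | not met | not met |
| 9, 8, 8 | 25 | 9 | met | met | not met |
| 13, 5, 5 | 23 | 13 | not met | not met | met |

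- 8, 8, 8 is the plain contradiction: it qualifies in 3.1 and meets neither score trigger in 6.4.
- 12, 6, 6 meets no score trigger in 6.4 either. It leads to escalation there only if a discretionary rescue dose was given under 6.5.
- 9, 8, 8 passes the sum threshold in both. The remaining difference is that 3.1 states discretion and 6.4 does not.
- 13, 5, 5 qualifies only in 6.4. Because 3.1 is an overview, I treat its lack of the single-score and rescue triggers as an omission, not a contradiction.

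**4. Do other sections settle it?** Initiation (3.1, 6.1) uses at least 24 and at least 12, and rescue (6.5) uses at least 12. The strict inequalities in 6.4 therefore stand alone, but nothing says whether that is intended.

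**The case against.** The best defence on phenobarbital is to read the sections together: 3.2.4.3 gives the indication and 6.8 the regimen. An infant normally reaches the maximum only through successive escalations driven by symptoms or rescue doses, so the affected group is only those who become controlled at the last step. That narrows the group correctly. It does not remove the conflict, because 6.8 ties later phenobarbital increases to uncontrolled symptoms and ties reduction and stopping to scores. Only the start carries no such condition.

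On escalation, a reader might infer that 6.4 makes escalation mandatory and so contradicts the discretion in 3.1. The documents do not support that. Both sections say that advancement will take place; 3.1 adds discretion and 6.4 is silent. Section 6.4 also says that it aims to mimic clinical care. This part is an ambiguity, while the threshold at exactly 24 is a contradiction. Nor does the conflict extend into weaning: 6.6 has its own reversion rule (a sum of at least 28, at discretion) and says that a rescue dose in that period does not trigger escalation.

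It is also fair that the endpoint is exploratory, with no test or decision attached, and that NAS scores and treatment times are recorded (6.9). Control at the start of phenobarbital can therefore be examined afterwards, and the population PK model remains usable. The algorithm figures are not shown here, so staff may be working from a clear rule. A figure still could not make the text sections agree.

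**Conclusion.** Both conflicts are real and should be corrected. Neither threatens the primary pharmacokinetic objective.

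- **Phenobarbital:** 6.8 and 3.2.4.3 differ for infants controlled at the maximum. Each one moves the exploratory count by 1 of 10, and their expected number cannot be derived from the protocol.
- **Escalation before weaning:** 3.1 and 6.4 contradict each other at a sum of exactly 24 with no score above 12 and no rescue dose given. Whether discretion applies under 6.4 is unclear. This rests on reading the 3.1 threshold as a sum.

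Two further inferences are not supported. A reader might infer that 6.8 removes a promised period at the maximum without phenobarbital; the protocol promises none and plans sampling during co-administration. A reader might also infer that a rescue dose during weaning can break the daily maximum; Tables 1 and 5 present 75 mcg/kg/day as three scheduled doses of 25, and on that reading nothing is exceeded.

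**What to change.** 1. Reconcile 3.2.4.3 with 6.8 so that one condition for starting phenobarbital appears in both.
2. Make the endpoint label in 3.2.4.3 follow the rule kept. If phenobarbital starts on reaching the maximum, describe the endpoint as the number of infants receiving phenobarbital, that is, reaching the maximum. If unresolved symptoms are also required, keep the present label and have the sponsor state what counts as adequate resolution.
3. Reconcile 3.1 with 6.4: state the result at a sum of exactly 24, say explicitly that the three scores are summed, and say whether physician discretion applies.
4. Check that the algorithm figures show the same rules.

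Which clinical rule is kept in each case is for the sponsor. The cost is amendment wording only: no new patients, procedures or data fields, since scores, doses and phenobarbital times are already collected.

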#### 1.3.4.6 Cessation Buprenorphine Dose

In the BBORN trial, the cessation dose was within 10% of the initial dose. The mean dose at time of cessation was 5.3 mcg/kg, based upon actual weight at the time of cessation. No infants required readmission following discharge, however 44% required a rescue dose after scheduled dosing was completed. The current trial will define the cessation dose as the dose that is equal or less than the initial dose in mcg (and not a weight normalized dose of mcg/kg). Most infants will regain their birthweight at about the time for cessation. A simulation was performed to estimate the impact of the proposed cessation dose (Table 8). This simulation was based upon cessation of all dosing at the cessation dose without any extension of interval. Despite a higher cessation dose, the model predicted less of a need for rescue doses. Symptom driven administration of rescue doses ensure that there will not be inadequate treatment of symptoms, even if the precision of the modeled response is less than expected.

Table 8: Simulated Time to Wean (hours) with Varied Wean Rate

	BPHORE	BBORN
Initial dose (mcg/kg)	8	5.3
Cessation dose	$\leq 100\%$ of the initial dose	$\leq 110\%$ of the initial dose
Initial mean infant weight used in simulation (gm)	2988	2988
Simulated weight at cessation (gm)	2940	3010
Simulated dose at cessation (mcg)	27.1	18.1
Simulated normalized dose at cessation (mcg/kg)	9.3	6.1
Simulated % of infants who would require post cessation rescue dose	25%	39%
Actual % of infants in BBORN requiring post cessation rescue dose	N/A	44%
Actual median birthweight in BBORN (gm)	N/A	3040

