### 5.2.2 *Phenobarbital*

The hospital standard of care phenobarbital elixir formulation (20 mg/5 ml or similar equivalent) will be used. Birth weight will be used for the calculation of phenobarbital loading and maintenance dose. A loading dose 20 mg/kg followed by daily oral dose of 5 mg/kg/day will be used. When buprenorphine is weaned to 50% of highest dose, phenobarbital is decreased to 2.5 mg/kg/day. After three additional opioid weans, phenobarbital will be discontinued and the buprenorphine weaned until cessation dose was met.

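### Section 6.8 gives the phenobarbital target as 20-40 mg/dL; the protocol's own doses fit mg/L, so the printed target is ten times too high

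*Protocol*

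**What the plan says.** Section 6.8 brings in phenobarbital once buprenorphine has reached its maximum of 75 mcg/kg/day: "phenobarbital will be initiated with a loading dose of 20 mg/kg followed by 5 mg/kg/day". Section 5.2.2 gives the same regimen: "A loading dose 20 mg/kg followed by daily oral dose of 5 mg/kg/day will be used".

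The next step in section 6.8 is conditional: "If symptoms of NAS are not controlled with phenobarbital 5 mg/kg/day", the dose can be "titrated up by the treating physician to a serum concentration of 20-40 mg/dL". The sentence after it covers the same situation and leaves more freedom: "the attending physician may adjust the dose clinically as needed, with or without the use of phenobarbital therapeutic drug monitoring".

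Section 6.8 also says that the neonatal half-life "decreases from 115 hr after 1 week to 67 hr after 4 weeks", and that phenobarbital is later cut to 2.5 mg/kg/day as buprenorphine is weaned.

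No other section gives a phenobarbital level, a different unit, a volume of distribution or a maximum phenobarbital dose.

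**The concern.** A target of 20-40 mg/dL is 200-400 mg/L, ten times the same digits in mg/L. A level to be reached after 5 mg/kg/day has failed should lie somewhat above what that dose gives, so a gap alone proves nothing. What matters is whether the gap is of a plausible size.

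The stake is safety. The infants concerned are at the maximum buprenorphine dose, where section 6.8 bars further buprenorphine rescue doses. Section 8 names respiratory depression and excessive sedation as the theoretical risks of opioid treatment. The range in section 6.8 is the only number that guides phenobarbital up-titration, and an error upward leads towards overdose. Table 9 schedules blood draws for periods of phenobarbital co-administration, so the protocol expects that some infants will receive it.

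**Working it through.** **Inputs from the protocol**
- Load 20 mg/kg, then 5 mg/kg/day (sections 5.2.2 and 6.8).
- Half-life 115 h after 1 week and 67 h after 4 weeks (section 6.8).
- Printed target 20-40 mg/dL = 200-400 mg/L (section 6.8).
- Elixir 20 mg/5 mL = 4 mg/mL (section 5.2.2).
- Mean infant weight 2988 g (section 1.3.4.6, Table 8).

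**Assumptions**
- One compartment and complete absorption. Lower absorption would widen the gap.
- The volume of distribution V is not in the protocol. It is first solved for, then varied.

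**Step 1: amount in the body.** Average steady-state amount = (5/24) × t½ / ln 2.
- 67 h: 0.2083 × 67 / 0.6931 = 20.1 mg/kg
- 115 h: 0.2083 × 115 / 0.6931 = 34.6 mg/kg
- Load: 20 mg/kg

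**Step 2: largest V that gives the printed target.** V = amount / concentration.

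| Source | 200 mg/L (20 mg/dL) | 400 mg/L (40 mg/dL) |
|---|---|---|
| Load | 0.100 L/kg | 0.050 L/kg |
| 5 mg/kg/day, 67 h | 0.101 L/kg | 0.050 L/kg |
| 5 mg/kg/day, 115 h | 0.173 L/kg | 0.086 L/kg |

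Using the peak of load plus daily doses (22.7 and 37.1 mg/kg) instead of the average moves the 200 mg/L limits only to 0.114 and 0.186 L/kg.

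**Step 3: levels over an assumed range of V.** Level = amount / V.

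| Assumed V (L/kg) | Load (mg/L) | Steady state, 67 h to 115 h (mg/L) |
|---|---|---|
| 0.3 | 66.7 | 67.1 to 115.2 |
| 0.5 | 40.0 | 40.3 to 69.1 |
| 1.0 | 20.0 | 20.1 to 34.6 |
| 1.2 | 16.7 | 16.8 to 28.8 |

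For V of 0.5-1.2 the doses give 17-69 mg/L, or 1.7-6.9 mg/dL. The printed lower limit is 200/69.1 = 2.9 to 200/16.7 = 12 times higher. At V = 0.3 it is still 200/115.2 = 1.7 to 200/66.7 = 3.0 times higher.

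**Step 4: dose needed to hold 200 mg/L.** Dose = 200 × V × (ln 2 / t½) × 24.
- V = 0.5: 14.5 (115 h) to 24.8 (67 h) mg/kg/day
- V = 1.2: 34.7 (115 h) to 59.6 (67 h) mg/kg/day

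For a 2.988 kg infant, 14.5 to 59.6 mg/kg/day is 43 to 178 mg/day, or about 11 to 45 mL/day of elixir. At 5 mg/kg/day it is 5 × 2.988 / 4 = 3.7 mL/day.

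**Step 5: the wean.** A cut to 2.5 mg/kg/day halves a dose of 5. From 14.5 it would be a single cut of 1 − 2.5/14.5 = 83%, and from 59.6 one of 96%. The wean step therefore also presupposes a dose near 5 mg/kg/day.

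**Step 6: the same digits in mg/L.** A level of 20-40 mg/L follows for V of 0.50-1.00 (load), 0.50-1.01 (67 h) and 0.86-1.73 L/kg (115 h). At V = 0.9, holding 20-40 mg/L needs 2.6-5.2 mg/kg/day (115 h) or 4.5-8.9 mg/kg/day (67 h), the same order as the stated 5.

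**The case against.** The strongest case concerns the likelihood of harm rather than the unit.

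- **The range does not bind.** It is permissive, the following sentence allows adjustment without drug levels, and up-titration depends on uncontrolled symptoms. The doses in Step 4 are what the printed level would require, not what one would expect to see. Physicians may well notice the slip, and section 8 provides telemetry until stabilization and round-the-clock senior cover. All of this stands and lowers the risk.
- **The multiples rest on an assumed V.** This is true, and at V = 0.3 L/kg the gap shrinks to 1.7-3 times. What the protocol's numbers establish alone is the limit of 0.10-0.17 L/kg. Calling such a volume implausible is an assumption, although the wean step points the same way without drawing on the load or maintenance levels.
- **The fit in mg/L is loose.** All three calculations fall within 20-40 mg/L only for V of 0.86-1.00 L/kg. At 115 h and V below 0.86 L/kg, 5 mg/kg/day alone would exceed 40 mg/L. So the doses overlap the range rather than match it.
- **Full steady state at 115 h would not be reached.** Four to five half-lives take 19-24 days, while the half-life falls to 67 h by 4 weeks. This is correct, but it lowers the attainable level and so widens the gap to mg/dL.
- **Few infants are exposed.** Only those among 10 who reach the buprenorphine maximum and then fail 5 mg/kg/day are concerned. This stands too.

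None of these points supports mg/dL as the intended unit.

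**Conclusion.** The target is wrong as written. As printed, it is out of reach of the stated load and maintenance dose unless V is at most 0.10-0.17 L/kg (0.11-0.19 using peaks). Over an assumed V of 0.5-1.2 L/kg it lies about 3-12 times above what those doses give. In mg/L the same digits overlap what they give, and they agree with the later wean to 2.5 mg/kg/day. The limit on V needs only the protocol's figures, a one-compartment model and complete absorption; the multiples also need the assumed V.

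The consequence is one of safety only, since no endpoint, sample size or analysis changes. It still has to be corrected: it is an operative dosing instruction for neonates at the maximum opioid dose, and its safety should not depend on the reader recognising the error.

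**What to change.** In section 6.8, replace 20-40 mg/dL with 20-40 mg/L (mcg/mL). This is one unit in an amendment and adds no samples, blood or data items.

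There is one trade-off. With the corrected unit, an infant with a long half-life may already be within or above the range on 5 mg/kg/day, which leaves little room for level-guided increases. The existing provision for clinical adjustment in section 6.8 still covers that infant.

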## 6.9 Study Data

The following elements will be collected in the study data base:

- mode of birth
- gestational age
- gender
- Apgar scores
- NAS scores
- birth weight
- daily weight
- daily intake (cc/kg/day) and type of feed
- stool number and characteristics
- head circumference
- concomitant medication
- urine drug screen results
- dates and times of primary treatment and phenobarbital (if applicable)
- medical record number
- adverse events
- respiratory patterns

Maternal elements to be collected include:

- opioid (methadone, buprenorphine, or other) dose
- urine drug screen
- tobacco use (none,  $\leq 5$  cigarettes/day,  $> 5$  cigarettes/day)
- concomitant medication during gestation
- medical record number
- date of birth

